7.11.2 Missing Dates

As a general rule, the worst case scenario imputation rule is usually used. A start date is generally imputed to the first possible day, unless the available information in the partly missing date is equal to the one in the reference date. In this case, the substituted date is set to the reference date. An end date is generally imputed to the last possible day.

Completely missing dates will not be imputed.

Diagnosis of anemia, CKD and Targeted Medical History

The following rules will be applied to impute partially missing dates of diagnosis of Anemia, CKD and targeted medical history, as defined in Table 27 below.

Table 27 Definitions of the Analysis Date of Diagnosis of Anemia, CKD and Targeted Medical History

Reported Date (from the eCRF)	Analysis Date (Derived)
--/MM/YYYY	01/MM/YYYY
--/--/YYYY	01/01/YYYY
DD/--/----, or --/MM/----, or --/--/----	No imputation

Previous or Concomitant medication:

For previous or concomitant medications, including rescue medications, partially missing start dates and/or stop dates will be imputed as defined in Table 28 and Table 29 below:

Table 28 Definitions of the Previous or Concomitant Medication Analysis Start Date

Reported Date (from the eCRF)	Analysis Date (Derived)
--/MM/YYYY	01/MM/YYYY
--/--/YYYY	01/01/YYYY
DD/--/----, or --/MM/----, or --/--/----	No imputation

If the imputed start date is after the stop date, then the imputed start date will be one day prior to the stop date.

Table 29 Definitions of the Previous or Concomitant Medication Analysis Stop Date

Reported Date (from the eCRF)	Analysis Date (Derived)
--/MM/YYYY	31/MM/YYYY, or 30/MM/YYYY, or 29/MM/YYYY, or 28/MM/YYYY
--/--/YYYY	31/12/YYYY
DD/--/----, or --/MM/----, or --/--/----	No imputation

AE Onset date

For adverse events, partially missing start dates and/or stop dates will be imputed as defined in [Table 30](#) and [Table 31](#) below:

Table 30 Definitions of the Analysis Adverse Event Onset Date

Reported Date	Date of First Drug Intake	Analysis Date (Derived)
--/MM/YYYY	DD/MM/YYYY	
--/02/2008	14/02/2008	14/02/2008*
--/02/2008	14/02/2007	01/02/2008
--/02/2008	14/02/2009	01/02/2008
--/--/YYYY	DD/MM/YYYY	
--/--/2008	14/02/2008	14/02/2008
--/--/2008	14/02/2007	01/01/2008
--/--/2008	14/02/2009	01/01/2008
DD/--/---- --/MM/---- --/--/----		No imputation

* If the month and year is the same as the month and year of first drug intake, use date of the first drug intake.

Table 31 Definitions of the Analysis Adverse Event End Date

Reported Date	Analysis Date (Derived) *
--/MM/YYYY	31/MM/YYYY or 30/MM/YYYY or 29/MM/YYYY or 28/MM/YYYY
--/--/YYYY	31/12/YYYY
DD/--/----, or --/MM/----, or --/--/----	No imputation

*Death has to be taken into consideration when calculating this.

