### 3.3 Exclusion Criteria

Subject will be excluded from participation if any of the following apply:

1. Subject has received a Red Blood Cell (RBC) transfusion within 8 weeks prior to randomization.
2. Subject has a known history of myelodysplastic syndrome or multiple myeloma.
3. Subject has a known hereditary hematologic disease such as thalassemia or sickle cell anemia, pure red cell aplasia, or other known causes for anemia other than CKD.
4. Subject has a known hemosiderosis, hemochromatosis, coagulation disorder, or hypercoagulable condition.
5. Subject has a known chronic inflammatory disease that could impact erythropoiesis (e.g., systemic lupus erythematosus, rheumatoid arthritis, celiac disease) even if it is currently in remission.
6. Subject is anticipated to undergo elective surgery that is expected to lead to significant blood loss during the study period or anticipated elective coronary revascularization.
7. Subject has active or chronic gastrointestinal bleeding.
8. Subject has received any prior treatment with roxadustat or a hypoxia-inducible factor prolyl hydroxylase inhibitor.
9. Subject has been treated with iron-chelating agents within 4 weeks prior to randomization.
10. Subject has a history of chronic liver disease (e.g. cirrhosis or fibrosis of the liver).
11. Subject has known New York Heart Association Class III or IV congestive heart failure.
12. Subject has had a myocardial infarction, acute coronary syndrome, stroke, seizure, or a thrombotic/thrombo-embolic event (e.g., deep vein thrombosis or pulmonary embolism) within 12 weeks prior to randomization.
13. Subject has had uncontrolled hypertension, in the opinion of the investigator, within 2 weeks prior to randomization.
14. Subject has known hypersensitivity to epoetin alfa (Eprex®), darbepoetin alfa (Aranesp®) or any of their excipients.
15. Subject has a diagnosis or suspicion (e.g., complex kidney cyst of Bosniak Category 2F or higher) of renal cell carcinoma as shown on renal ultrasound, or another appropriate imaging method, within 12 weeks prior to randomization.
16. Subject has a history of malignancy, except for the following: cancers determined to be cured or in remission for  $\geq 5$  years, curatively resected basal cell or squamous cell skin cancers, cervical cancer in situ, or resected colonic polyps.

17. Subject is positive for any of the following:
  - human immunodeficiency virus (HIV)
  - hepatitis B surface antigen (HBsAg), or

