In case of missing dates, the hospitalization duration will be imputed by the average duration per stay derived from the subjects with non-missing duration within the same treatment group. Duration of treatment exposure is defined in Section [6.5.4](#)

If the date of admission of a hospitalization record is the same as the date of discharge of the previous record, for example because two records are created to illustrate that the subject is moved from one hospital to another hospital or from a standard care to the intensive care unit (ICU), then the two records will be combined in one record.

Hospitalizations will also be described by reason for admission (admission for anemia or other reasons).

Time to first hospitalization in years will be defined in years as:

$(\text{First event date during the Efficacy Emergent Period} - \text{Analysis date of First dose intake} + 1) / 365.25$

With 'First event date' defined as 'Date of first Admission and 'Analysis Date of first dose intake' defined in Section [6.5.4](#)

For a subject without hospitalization, the time to censoring will be calculated as:

$(\text{Date of End of Efficacy Emergent Period} - \text{Analysis Date of first dose intake} + 1) / 365.25$

With date of End of Efficacy Emergent Period defined in Section [7.11.6](#)

6.1.3.7 Occurrence and time to first use of rescue therapy, occurrence and time to first use of RBC transfusions, number of RBC packs per subject, volume of RBC transfused per subject during the treatment period.

Rescue therapy is defined as RBC transfusion for all subjects and ESA (SC or IV) for roxadustat-treated subjects.

RBC transfusion is collected and coded into the ATC and WHO-DRL dictionaries. The following WHO-DRL codes will be classified as RBC transfusion: '01186901001'. ESA rescue treatment is recorded on the dosing CRF.

Only rescue medication that started during the study treatment and up to end of efficacy emergent period will be taken into account and considered as use of rescue medication.

For a subject with use of rescue therapy, the time to first use of rescue therapy will be calculated (in years) as:

$$(\text{First event date} - \text{Analysis Date of first dose intake} + 1) / 365.25$$

With 'First event date' defined as 'Date of first dose of rescue medication' during the Efficacy Emergent Period and 'Analysis date of first dose intake' defined in Section 6.5.4

For a subject without use of rescue therapy, the Time to censoring is calculated as:

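### SAP Table 28 has no Day 1 floor for partial rescue start dates, so an on-study transfusion can be imputed before first dose and dropped from the rescue endpoints

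*SAP*

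**What the plan says.** SAP 7.11.2 opens with a worst-case principle. A partial start date goes to the first possible day, "unless the available information in the partly missing date is equal to the one in the reference date". For the matching case it adds: "In this case, the substituted date is set to the reference date".

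The section then gives specific tables. Table 30 (adverse event onset) writes the exception out, with worked rows and the footnote "If the month and year is the same as the month and year of first drug intake, use date of the first drug intake". Table 28 ("Definitions of the Previous or Concomitant Medication Analysis Start Date") does not. It maps --/MM/YYYY to 01/MM/YYYY and --/--/YYYY to 01/01/YYYY, and has no column for first drug intake. Its scope is explicit: "For previous or concomitant medications, including rescue medications, partially missing start dates and/or stop dates will be imputed as defined in" Tables 28 and 29. Its only added condition concerns the stop date: "If the imputed start date is after the stop date, then the imputed start date will be one day prior to the stop date".

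SAP 6.1.3.7 decides which records count: "Only rescue medication that started during the study treatment and up to end of efficacy emergent period will be taken into account". The same section says that transfusions are coded as medications, while rescue ESA is recorded on the dosing CRF. SAP 7.11.1 sets Hb to missing for 6 weeks from the start of rescue, or from its end if it lasted more than one day.

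**The concern.** Two instructions in one section give different dates for the same record. The table is the more specific, and it is what a programmer would normally code. Under it, a transfusion given on study can acquire a pre-study start date and so fail the test in 6.1.3.7. At stake are the number of subjects with rescue therapy or transfusion, the two time-to-first-event analyses, and the pack and volume totals. For those endpoints, losing the record is the opposite of the worst case that the section says it follows.

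**Working it through.** **1. Reproduce Table 30, then run Table 28 on the same dates.** The general rule is: if the known part equals that of first drug intake, use first drug intake; otherwise use the first possible day. Study day is the date minus first intake, plus 1 if on or after first intake.

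| Reported | First intake | Table 30 prints | General rule | Table 28 | Study day under Table 28 |
|---|---|---|---|---|---|
| --/02/2008 | 14/02/2008 | 14/02/2008 | 14/02/2008 | 01/02/2008 | -13 |
| --/02/2008 | 14/02/2007 | 01/02/2008 | 01/02/2008 | 01/02/2008 | 353 |
| --/02/2008 | 14/02/2009 | 01/02/2008 | 01/02/2008 | 01/02/2008 | -379 |
| --/--/2008 | 14/02/2008 | 14/02/2008 | 14/02/2008 | 01/01/2008 | -44 |
| --/--/2008 | 14/02/2007 | 01/01/2008 | 01/01/2008 | 01/01/2008 | 322 |
| --/--/2008 | 14/02/2009 | 01/01/2008 | 01/01/2008 | 01/01/2008 | -410 |

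All six rows of Table 30 reproduce. Table 28 departs only in the two rows where the known part matches first intake, and both times it lands before Day 1.

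**2. Which on-study transfusions are exposed.** Month-only: those in the calendar month of Day 1. With Day 1 on the 2nd of a 31-day month, the last such day is study day 30. Year-only: those in the calendar year of Day 1.

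**3. Scale.** Assume Day 1 is uniform over the calendar and transfusions are uniform over follow-up. The documents supply neither.
- Month-only: for a month of length L, the mean number of exposed days is (L - 1)/2. The day-weighted mean of L is 30.46, so (30.46 - 1)/2 = 14.73 days. Dividing by 252, 364 and 728 days gives 5.8%, 4.0% and 2.0% of transfusion days over 36, 52 and 104 weeks.
- Year-only: over 52 and 104 weeks, (365.25 - 1)/2 = 182.1 days, which is 50% and 25%. Over 36 weeks, [252 x 253/2 + 112.25 x 252]/(365.25 x 252) = 60,165/92,043 = 65%.

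These are shares of records that already have a partial date, not of all transfusions.

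**4. The weeks 22 to 36 rescue window (SAP 6.1.1.1 and 6.1.2.1).** It starts 22 x 7 = 154 days after Day 1, well beyond day 30, so a month-only date in it cannot precede Day 1 (0%). A year-only date can if Day 1 is no later than about 30 July (30 July plus 154 days is 31 December). The mean day in the window is (154 + 252)/2 = 203, so the share is (365.25 - 1 - 203)/365.25 = 161.25/365.25 = 44% of year-only records.

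**5. What a Day 1 floor does to the Hb blanking.** Take first dose on 10 March 2016 and a transfusion in September 2016 recorded as --/--/2016. Table 28 gives 1 January 2016; the floor gives 10 March 2016. Blanking from the start then runs 42 days, to about 21 April. Week 28 is 196 days after first dose, 22 September. The weeks 28 to 36 average is therefore not blanked in either case, unless a known stop date moves the 6 weeks.

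**6. Eligibility.** Exclusion 1 reads: "Subject has received a Red Blood Cell (RBC) transfusion within 8 weeks prior to randomization". A month-only date moved to the first of the Day 1 month is at most 30 days before Day 1, inside the 56 days, so it can suggest a violation that did not happen. A year-only date does so only if Day 1 is no later than about 26 February (1 January plus 56 days). In the step 5 example the gap is 69 days, outside the window.

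**The case against.** The best defence is that the general rule already contains the exception, so Table 28 is merely incomplete, and that exposure is tiny. Rescue details go into the eCRF (Protocol 5.1.5), Hb is measured before and after each transfusion, and visits are weekly to week 8 and two-weekly to week 36, so few partial dates should survive query. Rescue ESA is on the dosing CRF. A subject with another fully dated on-study rescue still counts as rescued. The point about size stands. The first point does not settle the matter: the general rule is worded as what is usually done, Table 28 is the specific instruction for rescue records, and Table 30 shows that the authors wrote the exception out where they wanted it.

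A reader might also infer more than the documents support:
- *That the EU primary result is distorted.* Month-only dates cannot reach the window. Also, neither 6.1.1.1 nor 7.11.1 cites the started-on-treatment filter of 6.1.3.7, so its effect on the blanking is an inference.
- *That the date rules only ever remove rescue.* Table 29 moves partial stop dates to the last possible day. A record with both dates --/--/2016 becomes 1 January to 31 December 2016 and, if treated as rescue, would extend blanking beyond weeks 28 to 36.
- *That the imputed date always contradicts eligibility.* It does so for month-only dates, but for year-only dates only when Day 1 falls early in the year.
- *That a floor costs nothing.* Protocol 5.1.3.1 records prior anemia treatment, including transfusions, over the 12 months before randomization, and those more than 8 weeks before are permitted. An unrestricted floor could turn one of them into a Day 1 rescue.

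**Conclusion.** The inconsistency is real. As written, Table 28 can remove an on-study transfusion from the occurrence and time-to-first analyses of rescue therapy and transfusion. The practical effect is small, probably a handful of records at most. That is a judgement, since the documents give no count of partial dates, and the shares in the working rest on uniform timing. The exposure is mainly transfusions. For the EU primary endpoint and the first key secondary test (Hb response) the issue reduces to year-only records with Day 1 and the transfusion in the same calendar year, and even there correcting the start date does not by itself correct the Hb blanking. No sample size, power or alpha figure is affected. This is a tidy-up worth making, not a threat to the main conclusions.

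**What to change.** Add to Table 28: for RBC transfusion and rescue records that do not come from the pre-study anemia treatment history and are not known to have ended before Day 1, set the start date to the date of first dose when the known month and year (or the year alone) equal those of first dose, as Table 30 does. List every such record. Where the month is unknown, use any known stop date for the 6-week Hb blanking, and state what is done when there is none.

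The cost is one table row, a listing and minor programming. The downside is small: a year-only event is dated early in the time-to-first-rescue analysis, by about six months in the September example. The SAP Introduction allows revision before database hard lock. After lock, the handling should be justified in the clinical study report.

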7.11.3 Outliers

As a general rule, all values, including outliers will be analyzed.

7.11.4 Visits Windows

The study protocol gives the overall study schedule and the permissible intervals for visits expressed as the number of days relative to the first study medication date (Day 1).

For all study assessments reported by visit, the value which assessment day is the latest collected within the corresponding analysis visit window will be used. If more than one value is collected that day, then the latest value will be used in the analysis.

Analysis Visit windows, as depicted in [Table 32](#) below, will be used for the following study assessments reported by visit:

- Central laboratory parameters (except Lipid Panel),
- Vital Signs,
- ECG parameters.

Table 32 Analysis Visit Windows

CRF Visit	Target Day ^a	Analysis Visit Windows Actual Assessment Day	Analysis Visit
Screening		Day -42 to Day -1	Screening
Day 1	Day 1	Day 1	Baseline
Week 1	Day 7 * (Week #) + 1	Day 2 to Day 11	Week 1
Week 2 – 7	Day 7 * (Week #) + 1	[Target Day ± 3]	Week 2 - 7
Week 8	Day 7 * (Week #) + 1	[Target Day – 3, Target Day + 6]	Week 8
Week 10 - 34	Day 7 * (Week #) + 1	[Target Day – 7, Target Day +6]	Week 10 - 34
Week 36	Day 7 * (Week #) + 1	[Target Day – 7, Target Day +13]	Week 36
Week 40 – 100	Day 7 * (Week #) + 1	[Target Day – 14, Target Day + 13]	Week 40 - 100
Week 104/EOT (for completers)	Day 7 * (Week #) + 1	[Target Day – 14, Target Day + 28]	Week 104
EOT Visit (for premature discontinuations)	NA	NA	Analysis Visit corresponding to the actual visit window
EOT + 2 Weeks Visit	14 Days after EOT Visit date	[DAY of EOT + 1, DAY of EOT +20]	EOT + 2 Weeks
EOS Visit	28 Days after EOT Visit date	[DAY of EOT + 21, DAY of EOT + 31]	EOS
Unscheduled	NA	NA	Analysis Visit corresponding to the actual visit window

^a: Relative to Day 1 (first dose date of study medication)

Analysis Visit windows, as depicted in [Table 33](#) below, will be used for the quality of life efficacy study assessments:

Table 33 Analysis Visit Windows for QoL

CRF Visit	Target Day ^a	Analysis Visit Windows Actual Assessment Day	Analysis Visit
Day 1	Day 1	Day 1	Baseline
Week 8	Day 7 * (Week #) + 1	[Target Day – 14, Target Day + 13]	Week 8
Week 12	Day 7 * (Week #) + 1	[Target Day – 14, Target Day + 27]	Week 12
Week 28	Day 7 * (Week #) + 1	[Target Day – 28, Target Day + 27]	Week 28
Week 36	Day 7 * (Week #) + 1	[Target Day – 28, Target Day +27]	Week 36
Week 52	Day 7 * (Week #) + 1	[Target Day – 56, Target Day + 83]	Week 52
Week 76	Day 7 * (Week #) + 1	[Target Day – 84, Target Day + 97]	Week 76
Week 104/EOT (for completers)	Day 7 * (Week #) + 1	[Target Day – 98, Target Day + 28]	Week 104/EOT
EOT Visit (for premature discontinuations)	NA	NA	Analysis Visit corresponding to the actual visit window
Unscheduled	NA	NA	Analysis Visit corresponding to the actual visit window

^a: Relative to Day 1 (first dose date of study medication)

Analysis Visit windows, as depicted in [Table 34](#) below, will be used for the Lipid Panel, including LDL cholesterol efficacy study assessment:

Table 34 Analysis Visit Windows for Lipid Panel

CRF Visit	Target Day ^a	Analysis Visit Windows Actual Assessment Day	Analysis Visit
Day 1	Day 1	Day 1	Baseline
Week 4	Day 7 * (Week #) + 1	Day 2 to Day 42	Week 4
Week 8	Day 7 * (Week #) + 1	[Target Day – 14, Target Day + 13]	Week 8
Week 12	Day 7 * (Week #) + 1	[Target Day – 14, Target Day + 27]	Week 12
Week 20	Day 7 * (Week #) + 1	[Target Day – 28, Target Day + 27]	Week 20
Week 28	Day 7 * (Week #) + 1	[Target Day – 28, Target Day + 27]	Week 28
Week 36	Day 7 * (Week #) + 1	[Target Day – 28, Target Day + 27]	Week 36
Week 44	Day 7 * (Week #) + 1	[Target Day – 28, Target Day + 27]	Week 44
Week 52	Day 7 * (Week #) + 1	[Target Day – 28, Target Day + 55]	Week 52
Week 68	Day 7 * (Week #) + 1	[Target Day – 56, Target Day + 55]	Week 68
Week 84	Day 7 * (Week #) + 1	[Target Day – 56, Target Day + 69]	Week 84
Week 104/EOT (for completers)	Day 7 * (Week #) + 1	[Target Day – 70, Target Day + 28]	Week 104/EOT
EOT Visit (for premature discontinuations)	NA	NA	Analysis Visit corresponding to the actual visit window
EOS Visit	NA	Last assessment between Day 2 and study termination day	EOS
Unscheduled	NA	NA	Analysis Visit corresponding to the actual visit window

^a: Relative to Day 1 (first dose date of study medication)

For the MMRM analyses, which require one value per visit, one analysis value for each visit will be used.

For the ANCOVA analyses, which use the average, all available values in the analysis windows will be used for the calculation.

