2 FLOW CHART AND VISIT SCHEDULE

Flow Chart

Study Period: Visit/Week:	Screening Period			Treatment Period					Follow-up Period		Unscheduled Visits	Post study Follow up ^c
	2-6 Weeks ^a			Day 1 ^b	Weekly (Wks 1 to 8) ± 2 days	Every 2 Weeks (Wks 10 to 36) ± 2 days	Every 4 Weeks (Wks 40 to 100) ± 3 days	EOT ^c (Week 104) ± 3 days	EOT + 2 wks ± 3 days	EOS ^c (EOT + 4 wks) ± 3 days		Every 6 months until projected Wk 108
	S1	S2	S3									
Serum Lipid Panel ^l	X			X	Wks 4, 8	Wks 12, 20, 28, 36	Wks 44, 52, 68, 84	X		X	O	
Serum iron, ferritin, TIBC, TSAT ^m	X			X	Wks 4, 8	Wks 12, 20, 28, 36	Wk 44 + every other 8 wks	X		X	O	
HbA1c	X			X		Wk 12, 28, 36	Wks 44, 52, 60, 84	X		X	O	
Vitamin B ₁₂ , folate	X										O	
HIV, HBsAg, anti-HCV Antibody	X										O	
Serum Pregnancy Test (HCG) ⁿ	X					Wks 12, 24, 36	Wks 48, 60, 72, 84, 96	X			O	
high sensitivity C-reactive protein (hs-CRP), hepcidin				X	Wk 4	Wks 12, 20, 36	Wk 52	X		X		
Archival Serum Samples for Biomarkers				X	Wk 4	Wks 12, 20	Wks 52, 76	X		X		
Blood Sample for PK ^o					Wks 2 to 8							
QoL Questionnaires ^p				X	Wk 8	Wks 12, 28, 36	Wks 52, 76	X				
Dialysate ^q					Wks 2 to 8							
Optional genotyping ^r				O								
Study Treatment: roxadustat dispensing OR ESA administration ^s					-----						O	
Dose Adjustment Review ^t					X	X	X				O	
AE and Concomitant Medication Recording	←-----→											
Procedure and non-drug Therapy Recording	←-----→											
Vital status, SAEs, cardiovascular and thromboembolic AEs												X

Footnotes appear on next page

S1/S2/S3=Screening visit 1, 2 and 3; EOT = End of Treatment; EOS = End of Study; Wk(s) = Week(s); X = mandatory test/assessment; O = optional test/assessment. In HD subjects all lab sampling is to be performed prior to or at initiation of the dialysis session.

Note: Instructions for roxadustat-treated subjects moving from Protocol v1.0 to Protocol v2.0 in terms of dosing are provided in Protocol Appendix 12.3.

- ^a Due to the requirement of 4-day separation between the screening Hb values, the screening period will last a minimum of 2 weeks approximately, but is allowed to be a maximum of 6 weeks. Sites are recommended to schedule the three screening visits in the shortest time span possible.

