All available LDL values will be used (regardless the fasting status), i.e. both scheduled and unscheduled LDL values. LDL values in analysis visit windows at weeks 12, 20 and 28 will be selected for the calculation of the average LDL cholesterol of weeks 12-28 (see [Table 34](#) and Section [7.11.4](#) for the analysis windows definition and the differentiation between the MMRM and ANCOVA analyses).

For missing LDL imputation rules, refer to Section [7.11.1](#). Baseline LDL is defined as the LDL value on Day 1. If this value is missing, the latest value prior to first study drug administration will be used.

This analysis will also be repeated for fasted values only, as a sensitivity analysis.

6.1.2.3 Mean monthly IV iron use (mg) during day 1 to week 36

The Mean Monthly (defined as a period of 4 weeks or 28 days) IV iron use during day 1 to week 36, per subject (in mg) is defined by the following formula:

$$\frac{\text{Total IV iron use (mg) from Analysis date of first dose intake to Min (Analysis date of week 36 visit, End of Efficacy Emergent Period)}}{(\text{Min(Analysis date of Week 36 visit, End of Efficacy Emergent Period)} - \text{Day 1 date} + 1) / 28}$$

Analysis visits will be used as indicated in [Table 32](#), Section [7.11.4](#)

The use of IV iron is recorded in the *Concomitant Medication* form of the eCRF, where Route is INTRAVENOUS. All medications are coded with WHO-DD. Records selected will be those coded as IRON PREPARATIONS.

Having received IV iron is a binary variable (Yes/No), where “Yes” is defined as having at least one record selected during the Efficacy Emergent Period. Subjects using IV iron pre-treatment with an end date of Day 1 will not be included. Subjects without a relevant concomitant medication record will be assumed that they used no IV iron, thus set to 0 mg.

Time to first IV iron during day 1 to week 36 will be derived similarly to time to first occurrence of an increase in blood pressure, in Section [6.1.2.7](#) with first event date corresponding to the Date of first dose of IV iron during the day 1 to week 36 period. The time to censoring for a subject without the event of interest is calculated as:

$$(\text{Min (Week 36 analysis date, end of efficacy emergent period)} - \text{Analysis date of first dose intake} + 1) / 365.25$$

6.1.2.4 Change from BL in SF-36 Physical Functioning (PF) sub-score to the average PF sub-score of weeks 12 to 28.

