The use of IV iron is collected in the Concomitant Medication form of the eCRF. All medications are coded with WHO-DD. Records selected will be those coded as IRON PREPARATIONS, and where route is INTRAVENOUS.

Having received IV Iron is a binary variable (Yes/No), where “Yes” is defined as having at least one record selected during the Efficacy Emergent Period. Time to first IV Iron will be derived similarly to time to first use of rescue therapy, in Section [6.1.3.7](#) with first event date corresponding to the Date of first dose of IV Iron during the efficacy emergent period. Censoring rules will be the same as for use of rescue therapy.

The Efficacy Emergent Period will be divided in periods of 28 days and for each of these periods, the monthly mean of IV iron will be calculated. The total amount of IV iron used will be calculated for the overall Efficacy Emergent Period. Only use of IV Iron that was ongoing or started during the Efficacy Emergent Period will be taken into account.

The Mean Monthly IV iron use per subject (in mg) for weeks 37 to 52 and 53-104 will be calculated similarly as in Section [6.1.2.3](#). The occurrence of oral iron (coded as IRON PREPARATIONS and route ORAL) use will be also derived by the relevant periods (week 1-36, week 37-52, week 53-104) as a yes or no use of oral iron. This will be combined with IV iron use for these periods.

6.1.3.9 Change from BL to each post-dosing study visit in Total cholesterol, LDL/High-density Lipoprotein (HDL) ratio, Non-HDL cholesterol, Triglycerides, Apolipoproteins A1 and B, ApoB/ApoA1 ratio.

For each sample, the following will be calculated:

- LDL/HDL ratio (LDL Cholesterol divided by HDL Cholesterol)
- Non-HDL cholesterol (Total Cholesterol minus HDL Cholesterol)

Change from baseline to each post-dosing study visit will be calculated for the following lipid parameters:

- Total cholesterol
- LDL cholesterol
- HDL cholesterol
- Low-density lipoprotein (LDL) / high-density lipoprotein (HDL) ratio
- Non-HDL cholesterol
- Triglycerides
- Apolipoproteins A1 and B (ApoA1 and ApoB)
- ApoB/ApoA1 ratio.

All available data will be summarized descriptively for all parameters above, for fasted values and regardless of fasting status.

No imputation will be performed in case of a missing value. If several values are available in the same window, one value will be used, as defined in [Table 34](#) and Section [7.11.4](#)

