Descriptive statistics (value, change from baseline) by visit, treatment arm and type of ESA treatment will be presented regardless of fasting status, including averages in week 12-28. Descriptive statistics will also be reported with fasted values.

7.4.3.10 Occurrence of mean LDL cholesterol <100 mg/dL calculated over weeks 12 to 28.

The number and percentage of subjects with mean LDL cholesterol less than 100 mg/dL (2.59 mmol/L) (regardless fasting status) on average in weeks 12-28 will be reported by treatment arm and type of ESA treatment. Descriptive statistics and frequency tabulations will also be reported on fasted values, and regardless of fasting status.

7.4.3.11 Occurrence of achieved antihypertensive treatment goal in CKD subjects (SBP < 140 mmHg and DBP < 90 mmHg) based on the mean SBP and mean DBP calculated over weeks 12 to 28.

The number and percentage of subjects with achieved antihypertensive treatment goal over an evaluation period defined as the average of available values in weeks 12-28 will be reported by treatment arm and type of ESA treatment.

7.4.3.12 Health related Quality of Life Questionnaires Change from BL to the average value of weeks 12 to 28

The following questionnaires will be analyzed:

- SF-36 (Physical Component Score (PCS));
- FACT-An (Anemia Subscale (“Additional Concerns”), Total FACT-An Score);
- EQ-5D 5L (VAS Score);
- Patients’ Global Impression of Change (PGIC).

SF-36 and FACT-An

Descriptive statistics and frequency tabulations (value, change from baseline) will be presented for SF-36 (subscale and component scores) and FACT-An (total and subscale scores) by visit, treatment arm and type of ESA treatment. Mean values will also be plotted over time and by treatment arm.

In addition, for the average value in weeks 12-28, an inferential analysis, similar to the one defined in Section 7.4.1.1.1 will be performed for the following endpoints:

- Physical Component Scores of SF-36 (SF-36 PCS)
- Anemia Subscale (“Additional Concerns”) of FACT-An Scores
- Total FACT-An Scores
- Fatigue

For SF-36, at each visit, the frequency and proportion of subjects with a change from baseline ≤ 3 points and ≤ 5 points will be reported for Physical Functioning, Vitality and Physical Component scores.

In addition to this, change from BL to the average value of weeks 36 to 52 will be summarized similarly as for change from BL to the average value of week 12 to 28.

EQ-5D 5L

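### SAP Table 34 fills the lipid EOS visit with the last value from Day 2 onward, so some on-treatment values are tabulated as end-of-study values

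*SAP*

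**What the plan says.** SAP 7.11.4 has separate visit-window tables. Table 34 covers the lipid panel, and its EOS row takes the "Last assessment between Day 2 and study termination day". Nothing in that row refers to the EOT visit or to the last dose.

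Table 32 covers the other central laboratory parameters, vital signs and ECG. There the EOS target is "28 Days after EOT Visit date" and the window is "DAY of EOT + 21, DAY of EOT + 31".

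The flow chart in SAP section 2 labels the EOS column "EOT + 4 wks) ± 3 days". It schedules a lipid panel at EOT and again at EOS, with none at the visit two weeks after EOT.

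SAP 6.1.3.9 (lipid change from baseline by visit) sends the reader to Table 34 and states: "No imputation will be performed in case of a missing value". Where a window holds several values, SAP 7.11.4 says that "the value which assessment day is the latest collected within the corresponding analysis visit window will be used".

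The resulting output is set out in SAP 7.4.3.9: "Descriptive statistics (value, change from baseline) by visit, treatment arm and type of ESA treatment will be presented regardless of fasting status". A fasted-only version is also planned.

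**The concern.** The name EOS means one thing in the flow chart and Table 32 and another in Table 34. A reader of the by-visit lipid tables will take EOS to be a measurement about four weeks after EOT. Under Table 34 as written, a subject whose last lipid sample was at Week 12, or at EOT, is counted in that row. In effect the row carries the last observation forward without saying so, in an analysis that declares no imputation.

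The protocol lists an improved lipid profile and lower cholesterol among the expected advantages of roxadustat (sections 1.2.1 and 1.4). EOS is the only scheduled lipid sample in the follow-up period. At stake is whether the descriptive tables show that sample cleanly, and with the right number of subjects behind it.

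**Working it through.** The plan gives no figure to reproduce, so the check is window arithmetic and then a simple dilution formula.

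**Inputs.** Target day = 7 × week + 1 (SAP 7.11.4). EOS target = EOT + 28 and EOS window = EOT + 21 to EOT + 31 (Table 32). Lipid windows are from Table 34. EOT can fall from Week 52 to Week 104 (protocol 2.2.1.3).

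**Step 1: which values can be labelled EOS.** Table 34 admits any day from Day 2. For a completer with EOT on Day 729 (7 × 104 + 1), the scheduled EOS is Day 757. If that sample is missing, the value shown as EOS is the last one available:

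| Last lipid sample | Day | Days before scheduled EOS (Day 757) |
|---|---|---|
| Week 12 | 85 | 672 |
| Week 28 | 197 | 560 |
| Week 52 | 365 | 392 |
| Week 104/EOT | 729 | 28 |

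Under the Table 32 rule only Days 750 to 760 would qualify (729 + 21 to 729 + 31), and this subject would be missing at EOS.

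**Step 2: effect on the row.** Let m be the share of subjects in the EOS row whose value is carried from treatment. Assume that they resemble the others in their on-treatment level and in the change they would have shown. Then

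mean shown = (1 − m) × off-treatment mean + m × on-treatment mean,

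so the change from on-treatment shown at EOS is (1 − m) times the true change. The documents do not give m. For a range of assumed values:

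| Assumed m | Share of change visible | True EOS samples per 100 counted |
|---|---|---|
| 5% | 95% | 95 |
| 10% | 90% | 90 |
| 20% | 80% | 80 |
| 30% | 70% | 70 |
| 40% | 60% | 60 |

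If m differs between arms, so does the dilution.

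**Step 3: would changing the EOS row alone be enough?** Two Table 34 windows are relevant:

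- Week 104/EOT: 729 − 70 = Day 659 to 729 + 28 = Day 757. The EOS window for EOT on Day 729 is Day 750 to 760, so Days 750 to 757 belong to both.
- Week 52: 365 − 28 = Day 337 to 365 + 55 = Day 420. For EOT on Day 365, the EOS window is Day 386 to 396, wholly inside it.

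If windows are assigned by day alone, the latest-in-window rule lets the EOS sample (Day 757 or Day 393) displace the EOT value in the Week 104 or Week 52 row. Correcting only the EOS row would therefore leave follow-up values in rows read as on treatment. Table 32 has the same upper limit for Week 104 (target + 28).

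**The case against.** The strongest reply is that few subjects should be affected. EOS lipids are scheduled for everyone, and subjects who stop treatment early also complete an EOS visit (protocol 6.1, SAP 3.2.3). Anyone who has the EOS sample contributes it even under Table 34, because it is their last value. Those affected are mainly subjects who died, withdrew, were lost or were not sampled. Laboratory data are also listed individually (SAP 7.5.2), so carried values can be traced. All of this stands. A reader might infer that a rebound after stopping would be hidden. That is true only for an individual without the sample; the group mean is diluted in proportion to m.

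A second reply is that the row may have been meant as a last-value summary, in which case it is normal for a sample to appear there and under its own visit. That answers any complaint about double counting, but not the label. For PGIC (SAP 6.1.3.13) the SAP says explicitly that the last post-baseline score will be derived as well; it says nothing of the kind for lipids.

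Third, no objective or endpoint concerns reversal of lipid changes, and anemia treatment in follow-up is left to the investigator (protocol 2.2.1.3, SAP 3.2.3). ESA-arm subjects may still be on an ESA at EOS, and roxadustat subjects may have started one. A reader might treat EOS as a washout comparison between arms. The documents do not support that reading, even with the right window.

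**Conclusion.** The Table 34 EOS definition is wrong as written. It contradicts the flow chart, Table 32 and the no-imputation statement in SAP 6.1.3.9, and nothing elsewhere limits it to follow-up samples. The consequence is minor: a mislabelled row with an inflated n and a diluted post-treatment change, confined to descriptive lipid tables. At an assumed 10% to 30% of subjects without an EOS sample, 90% to 70% of any change would remain visible. This rests on the assumed share and on carried-forward subjects resembling the rest.

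Two stronger conclusions should not be drawn. A reader might infer that the LDL superiority claim is at risk. It does not depend on this row: SAP 6.1.2.2 states that "LDL values in analysis visit windows at weeks 12, 20 and 28 will be selected" for the average, and the LDL below 100 mg/dL endpoint uses the same period (SAP 6.1.3.10). A reader might also want the bias in mg/dL. That requires a difference between on-treatment and off-treatment LDL, which the documents do not give, so any such figure would be one assumption multiplied by another.

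**What to change.** Three changes to SAP 7.11.4:

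1. Set the Table 34 EOS row to EOT + 21 to EOT + 31 days, as in Table 32. Subjects without a sample there are then missing at EOS, in line with SAP 6.1.3.9.
2. If a last-value summary is wanted, give it a separate row labelled last post-baseline value.
3. State that, for the by-visit lipid tables, samples taken after the EOT visit are not assigned to on-treatment windows. Without this, the Week 52 window (to Day 420) and the Week 104/EOT window (to Day 757) still overlap the EOS window.

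The scope of the third change should be explicit. Applied to every lipid analysis, it would also remove some early stoppers' EOS samples from the Week 12 to 28 windows: EOT on Day 57 puts EOS on Day 85 (57 + 28), which is the Week 12 target day (7 × 12 + 1). Limiting it to the descriptive tables leaves the key secondary LDL analysis as planned.

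The cost is one table row, one optional extra row and one sentence. No new data are needed and no significance level changes. The EOS n will be smaller, because it will count only subjects sampled in that window.
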